1.2. Schema

1.3. Schedule of Activities (SoA)

Both treatment arms will use the same Screening Table ([Table 1](#)). Separate tables have been produced for the GSK3228836 treatment period ([Table 2](#) and [Table 3](#)). Both treatment arms will use the same PegIFN Treatment Table ([Table 4](#)), Reassessment of PegIFN Eligibility Tables ([Table 5](#) and [Table 6](#); only required if participant is ineligible to start PegIFN as per [Table 4](#)) and Off Treatment Follow-up Table ([Table 7](#)).

[China specific Schedule of Activities can be found in [Appendix 7: Country-specific requirements](#)]

Instructions that are applicable to all treatment arms include:

- In selected countries/sites, participants will have the option to use a centralised home nursing provider. Only selected visits will have the option to be performed as a home visit, these will include drug administration, blood draws, participant assessments and data collection. The full specifications of the home nursing services will be outlined in the Study Reference Manual (SRM).
- Haematology (platelet count) will be analysed at a local laboratory prior to each GSK3228836 dose. The blood draw can be taken the day before GSK3228836 dosing. Results must be available prior to dosing. Haematology samples will be collected for central laboratory assessments in parallel. After GSK3228836 treatment is completed, haematology is only collected centrally on weeks of clinic visits.
- If a participant is not eligible to start PegIFN, eligibility will be reassessed. If the participant does not become eligible after 13 weeks, PegIFN will not be initiated in order to ensure participants receive at least 12 weeks of PegIFN treatment. Irrespective of the week that a participant starts PegIFN, the final dose will be given on Study Week 48 for Arm 1 and Week 36 for Arm 2 ([Figure 1](#)).
- PegIFN dosing maybe self-administered at home, where local regulations allow at the visits indicated in the SoA ([Table 4](#)).

Figure 1 Schematic of Planned GSK3228836 and PegIFN Dosing Periods and Off Treatment Follow-up Period

[figure not shown]

Table 1 Screening (All Treatment Arms)

ASSESSMENTS	
Informed Consent (obtained any time prior to screening)	X
Inclusion and exclusion criteria	X
Demography	X
Medical history (includes substance usage) and current medical conditions	X
Medication history and concomitant medication review	X
Full physical exam including height and weight	X
Vital signs	X

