HBeAg (for participants HBeAg positive at screening)		X	X	X	X		X		X		X		X		X		X		X		X		X		X

PegIFN Dosing Week	1 ^a	2	3	4	5	6	7	8	9	10	11	12	13	14	15	16	17	18	19	20	21	22	23	24	
Window	±3 days																								
Complement C3, C4, C5a, Bb, hs-CRP, MCP-1			X		X				X					X			X				X				
ANCA, Ang II		X			X				X					X			X				X				
PK – PegIFN		X	X		X									X			X				X				
PK –GSK3228836		X		X							X			X											
HBV RNA, and sequencing (HBV genotype/phenotype; HBV DNA and/or RNA)		X	X		X			X		X				X			X				X				X
HBcrAg		X			X				X					X							X				
PBMC Collection for immunophenotyping ⁵		X			X									X											
Soluble Protein (immunology)		X	X		X									X			X				X				
PAXGene RNA for expression analysis in whole blood		X			X									X											
Archived Samples [serum; plasma]		X	X	X	X			X		X				X			X				X				X

- a. The first planned PegIFN visit occurs 7 days after the planned GSK3228836 dosing period.
- 1. Assessment of PegIFN eligibility should be based upon pre-dose safety assessments and laboratory assessments from previous visit
- 2. For specific Peg-IFN eligibility criteria please refer to protocol Section 4.1; **If ineligible for PegIFN refer to Table 5.**
- 3. If consistent with local regulations, participants are permitted to self-administer PegIFN at home, site staff may call to assess the participant by phone at this visit and no clinic visit is required. If local regulations or practices prefer to administer PegIFN within the clinic, this can be a clinic visit.
- 4. Participants in Japan are expected to return for a mid-week haematology assessment during Week 1 and at Week 5 and 7 in accordance with local regulations
- 5. Only for selected sites able to transport to the analysis lab as specified in the SRM

Table 5 Reassessment of PegIFN Eligibility

If a participant is ineligible for PegIFN dosing immediately (Week 1, [Table 4](#)), complete the SoA of PegIFN Eligibility Week 1, [Table 5](#).

Eligibility for PegIFN will be reassessed following the SoA in [Table 5](#) on PegIFN Eligibility Week 2, 3, 4, 6, 8, 10 and 13.

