If a participant becomes eligible for PegIFN during any of the reassessment visits, the SoA in [Table 4](#) should be followed starting at the Week 1 “Yes” column for the remainder of PegIFN dosing visits and stopping at the visit number where the combined PegIFN dosing and PegIFN eligibility visits equal “25” – for example, if a participant becomes eligible for PegIFN on PegIFN Eligibility Week 4, the SoA in [Table 4](#) should be followed from Week 1 to Week 21 ([Table 6](#)).

PegIFN Eligibility Week	1	2	3	4	5	6	7	8	9	10	11	12	13	14	15	16	17	18	19	20	21	22	23	24	
Window	±3 days																								
Eligible for PegIFN (Section 4.1)	No	No	No	No		No		No		No			No												
Clinic visit	X	X	X	X		X		X		X			X			X				X					X
Safety Assessments																									
AE/SAE review		X	X	X	X	X	X	X	X	X	X	X	X	X	X	X	X	X	X	X	X	X	X	X	X
Concomitant medication review		X	X	X	X	X	X	X	X	X	X	X	X	X	X	X	X	X	X	X	X	X	X	X	X
Symptoms directed exam		X	X	X		X		X		X			X			X				X					
Vital signs		X	X	X		X		X		X			X			X				X					X
Neuropsychiatric assessment (C-SSRS and BDI-II)		X	X	X		X		X		X			X												
Laboratory Assessments (If not Eligible to begin PegIFN treatment)																									
Pregnancy test (WOCBP)	X			X				X		X			X			X				X					X
Haematology [includes platelet and WBC with differential]	X	X	X	X		X		X		X			X			X				X					X
TSH, T4						X							X												X
PT, INR, aPTT	X			X									X			X				X					X
Chemistry	X	X	X	X		X		X		X			X			X				X					X
Urinalysis	X	X		X				X					X			X				X					X
Urine ACR	X	X		X				X					X			X				X					X
HBsAg and HBV DNA	X	X	X	X		X		X		X			X			X				X					X

PegIFN Eligibility Week	1	2	3	4	5	6	7	8	9	10	11	12	13	14	15	16	17	18	19	20	21	22	23	24
Window	±3 days																							
Anti- HBsAg and anti-HBeAg	X			X				X				X			X				X					X
HBeAg (for participants HBeAg positive at screening)	X	X	X	X		X		X		X		X			X				X					X
Complement C3, C4, C5a, Bb, hs-CRP, MCP-1		X		X				X				X			X				X					
ANCA, Ang II	X			X				X				X			X				X					
PK – GSK3228836	X		X			X				X		X												
HBV RNA and sequencing (HBV genotype/phenotype; HBV DNA and/or RNA)	X	X		X		X		X		X		X			X				X					X
HBcrAg	X			X				X				X							X					
PBMC Collection for immunophenotyping ¹												X												
Soluble Protein (immunology)												X												
PAXGene RNA for expression analysis in whole blood												X												
Archived Samples [serum; plasma]	X	X	X	X		X		X		X		X			X				X					X

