1. Only for selected sites able to transport to the analysis lab as specified in the SRM

Table 6 PegIFN Dosing for Participants becoming Eligible for PegIFN after Week 1

Become Eligible for PegIFN at PegIFN Eligibility Week (Table 5)	PegIFN Dosing (Table 4) should continue until PegIFN Dosing Week
2	23
3	22
4	21
6	19
8	17
10	15
13	12

Table 7 Off-Treatment Week (OTW) Follow-up: Week 1-24 (Treatment Arm 1) or Week 1-36 (Treatment Arm 2)

Assessments	OTW1 ^a	OTW2	OTW4	OTW8	OTW12	OTW18	OTW24	OTW30 ¹	OTW36 ¹	Early Termination
Window	±3 days									NA
Safety Assessments										
AE/SAE review	X	X	X	X	X	X	X	X	X	X
Concomitant medication review	X	X	X	X	X	X	X	X	X	X
Symptoms directed exam	X	X	X	X	X	X	X	X	X	X
Vital signs	X	X	X	X	X	X	X	X	X	X
Neuropsychiatric assessment (C-SSRS and BDI-II) ²	X		X	X	X		X			X
Laboratory Assessments										
Pregnancy test (WOCBP)	X		X	X	X	X	X	X	X	X
Haematology [includes platelet and WBC with differential]	X		X		X		X			X
PT, INR, aPTT	X		X		X		X			X
Chemistry	X	X	X	X	X	X	X	X	X	X
Urinalysis	X		X		X		X			X
Urine ACR	X		X		X		X			X
HBsAg and HBV DNA	X	X	X	X	X	X	X	X	X	X
Anti-HBsAg and anti-HBeAg	X		X	X	X	X	X	X	X	X
HBeAg (for participants HBeAg positive at screening)	X	X	X	X	X	X	X	X	X	X
Complement C3, C4, C5a, Bb, hs-CRP, MCP-1, ANCA, Ang II	X				X		X			X
PK for PegIFN ²	X	X	X	X						X
HBV RNA and sequencing (HBV genotype/phenotype; HBV DNA and/or RNA)	X	X	X	X	X	X	X	X	X	X
HBcrAg	X		X	X	X		X			X
PBMC Collection for immunophenotyping ³	X						X			X
PAXGene RNA for expression analysis in whole blood	X				X		X			X
Soluble Protein (immunology)	X		X		X		X			X
Archived Samples [serum; plasma]	X	X	X	X	X	X	X	X	X	X

- a. The first planned Off treatment visit occurs 7 days after the planned PegIFN dosing period.
- 1. Only applicable for Treatment Arm 2
- 2. Only for participants that received at least 1 dose of PegIFN.
- 3. Only for selected sites able to transport to the analysis lab as specified in the SRM.

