
Endocrine disorders:
 
Thyroid function abnormalities or worsening of pre-existing thyroid disorders
 
Hypoglycaemia/Hyperglycaemia/Diabetes Mellitus
	
Thyroid function abnormalities or worsening of pre-existing thyroid disorders have been reported with the use of alfa interferons, including PegIFN.
 
Hypoglycaemia, hyperglycaemia and diabetes mellitus have been observed with PegIFN.
	
Participants with uncontrolled thyroid function are excluded from this study. Thyroid function tests will be monitored as per the SOA. Abnormalities of thyroid function should be managed according to local guidance. If thyroid function cannot be adequately managed PegIFN treatment should be discontinued.
 
Participants with uncontrolled diabetes are excluded from this study. Blood glucose will be monitored throughout the study.

Potential Risk of Clinical Significance	Summary of Data/Rationale for Risk	Mitigation Strategy
		Abnormalities of blood glucose should be managed according to local guidance. If blood glucose cannot be adequately managed PegIFN treatment should be discontinued.
Cardiovascular disorders: Hypertension, supraventricular arrhythmias, congestive heart failure, chest pain and myocardial infarction	These have been associated with alfa interferon therapies, including PegIFN.	
Patients with significant/unstable cardiac disease are excluded from the study.
 
Participants will undergo an electrocardiogram (ECG) at screening and prior to PegIFN treatment.
 
If there is any deterioration of cardiovascular status, therapy should be suspended or discontinued.

Retinopathy including retinal haemorrhages, cotton wool spots, papilloedema, optic neuropathy and retinal artery or vein obstruction which may result in loss of vision	These have been reported in rare instances with PegIFN.	
All participants will have a baseline eye examination.
 
Any participant complaining of a change in vision or a new visual disturbance will have an urgent eye examination and PegIFN should be discontinued.

Fever/Infections	Serious infections (bacterial, viral, fungal) and sepsis have been reported during treatment with alfa interferons including PegIFN.	Appropriate anti-infective therapy should be started immediately, and discontinuation of PegIFN should be considered

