4.7.2. Other Endpoints / Variables

The following endpoints, in addition to primary endpoints, will be summarised using descriptive statistics by treatment arm. All of the endpoints below except for 8,13, and 14-21 are also included and defined in the end of study analyses.

- 1) Summary of proportion of participants who achieve HBsAg <LLOQ and HBV DNA <LLOQ over time.

- 2) Summary of proportion of participants who achieve HBsAg <LLOQ and HBV DNA <LLOQ at end of treatment by baseline stratification.
- 3) Summary of proportion of participants who achieved <0.5 , ≥ 0.5 , ≥ 1 , ≥ 1.5 , ≥ 3 log₁₀ IU/mL decline in HBsAg over time by baseline stratification.
- 4) Summary of proportion of participants who achieved <1 , ≥ 1 , ≥ 2 , ≥ 3 log₁₀ IU/mL decline in HBV DNA over time by baseline stratification.
- 5) Summary of actual values and change from baseline over time of HBsAg (log₁₀ IU/mL) and HBV DNA (log₁₀ IU/mL).
- 6) Summary of actual values and change from baseline over time of HBsAg (log₁₀ IU/mL) and HBV DNA (log₁₀ IU/mL) by genotype.
- 7) Summary of HBe antibody (anti-HBeAg) levels over time in HBeAg positive participants.
- 8) Summary of HBe antibody (anti-HBeAg) levels over time in HBeAg positive participants who achieve SVR.
- 9) Summary of actual values and change from baseline over time of HBs antibody (anti-HBsAg).
- 10) Summary of HBs antibody (anti-HBsAg) levels over time.
- 11) Summary of HBs antibody (anti-HBsAg) levels over time in participants who achieve SVR.
- 12) Proportion of participants who achieved ALT normalization with Baseline ALT >ULN over time.
- 13) Summary of proportion of participants who achieved HBV DNA TND over time.
- 14) Summary of concordance of an early virologic response with achieving SVR at PegIFN on-treatment visits Week 6, Week 13, Week 16, Week 20, and Week 24.
- 15) Association between HBV DNA 'Target Not Detected' and relapse in participants who achieve virologic response at end of treatment.
- 16) Summary of ROC analysis for baseline HBsAg as a predictor of SVR in participants who reached end of off-treatment follow-up (EoT+24wks) by IA.
- 17) Summary of baseline characteristics for responders and non-responders.
- 18) Summary of SVR rates for variables potentially associated with response.
- 19) Statistical analysis of variables associated with SVR success - logistic regression – all arms.

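### Participants who start PegIFN late never reach the Week 24 TSH/T4 test, and no later scheduled thyroid test takes its place

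*Protocol*

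**What the plan says.** Protocol Section 2.3.1 lists thyroid dysfunction as a PegIFN risk. Part of the mitigation reads: "Thyroid function tests will be monitored as per the SOA".

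The schedule in Section 1.3 works as follows.

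- Table 4 (PegIFN treatment) marks TSH/T4 three times. The last mark is in the final column, Dosing Week 24.
- Participants not eligible at once are reassessed "on PegIFN Eligibility Week 2, 3, 4, 6, 8, 10 and 13". On becoming eligible they enter Table 4 at Week 1 and leave it "stopping at the visit number where the combined PegIFN dosing and PegIFN eligibility visits equal" 25. In the protocol's example, eligibility at Week 4 means that Table 4 "should be followed from Week 1 to Week 21".
- Table 6 sets this out under the column heading "PegIFN Dosing (Table 4) should continue until PegIFN Dosing Week": 23, 22, 21, 19, 17, 15 and 12.
- The calendar end of PegIFN is fixed whatever the start: "the final dose will be given on Study Week 48 for Arm 1 and Week 36 for Arm 2".
- Table 5 has its own TSH/T4 row, but its laboratory block applies to participants who are not eligible to begin PegIFN.
- Table 7 (off-treatment follow-up and Early Termination) has no TSH/T4 row.

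**The concern.** The end-of-course thyroid test is attached to a column number and not to the end of the participant's PegIFN. A late starter leaves Table 4 before that column, and Table 7 supplies no substitute.

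This looks like a by-product of how the tables join. Haematology, chemistry, coagulation, urinalysis and the neuropsychiatric scales all recur at Off-Treatment Week 1, so a late starter still has an end-of-PegIFN value for each; thyroid function is the exception. A participant who never receives PegIFN keeps a last-column TSH/T4 in Table 5, while one who receives up to 23 weeks of it has no end-of-course test.

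Two things are at stake. A thyroid change without symptoms that arises after mid-course may go unseen in late starters. And Protocol Section 9.4.4 summarises laboratory data by visit, so a thyroid summary at Dosing Week 24 would describe on-time starters only, with nothing in the table to say so.

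**Working it through.** **Inputs.** Eligibility week E takes the values 2, 3, 4, 6, 8, 10 and 13 (text above Table 5). The stop rule sets eligibility plus dosing visits to 25. The TSH/T4 weeks come from Table 4.

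**Step 1: reproduce Table 6.** Last dosing week L = 25 − E. All seven entries agree, and all are below 24.

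**Step 2: locate the TSH/T4 marks.** In the extracted Table 4 they fall in columns 6, 13 and 25 of 25. Dosing Week 1 occupies two columns (eligibility check, then first dose), so a literal count gives Weeks 5, 12 and 24. Weeks 6, 13 and 24 are better supported:

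- In the dosing row, the weeks without the home-administration footnote are 1, 2, 3, 4, 6, 8, 10, 13, 16, 20 and 24. Weeks 5 and 12 carry the footnote.
- Those weeks match the clinic visits in Table 5, whose own TSH/T4 marks sit at 6, 13 and 24.
- SAP 4.7.2 refers to "PegIFN on-treatment visits Week 6, Week 13, Week 16, Week 20, and Week 24".

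The extracted clinic-visit row of Table 4 does not match the dosing row: counted literally, it has a visit at Week 12 and none at Week 5 or 13. Both readings are therefore shown.

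**Step 3: weeks from last scheduled test to last planned dose.** Gap = L minus the latest test week not after L.

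| E | L = 25 − E | Table 6 | Last test (6/13/24) | Gap | Last test (5/12/24) | Gap |
|---|---|---|---|---|---|---|
| 1 (on time) | 24 | n/a | 24 | 0 | 24 | 0 |
| 2 | 23 | 23 | 13 | 10 | 12 | 11 |
| 3 | 22 | 22 | 13 | 9 | 12 | 10 |
| 4 | 21 | 21 | 13 | 8 | 12 | 9 |
| 6 | 19 | 19 | 13 | 6 | 12 | 7 |
| 8 | 17 | 17 | 13 | 4 | 12 | 5 |
| 10 | 15 | 15 | 13 | 2 | 12 | 3 |
| 13 | 12 | 12 | 6 | 6 | 12 | 0 |

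The range is 2 to 10 weeks on the better reading and 0 to 11 on the literal one. The missed Week 24 test does not depend on the reading.

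**Step 4: compare with the planned interval.** On-time starters go 24 − 13 = 11 weeks between their last two tests (24 − 12 = 12 on the literal count). The longest late-starter gap is 23 − 13 = 10 (or 23 − 12 = 11). The on-drug gap is therefore never longer than the interval the plan already accepts. The difference is what follows: an on-time starter's interval ends with a test, and a late starter's does not.

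**Step 5: check the reporting.** Protocol Table 17 lists TSH/T4 among other tests, outside chemistry and haematology. In SAP 4.5.3.1 the toxicity-grade shift tables cover chemistry and haematology. The period-specific shift summaries also name urinalysis and immunology. None names thyroid function. Laboratory values outside the normal range are to be summarised and listed.

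**The case against.** The strongest reply is that only one routine test is missing.

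- A reader might infer that late starters go unmonitored for thyroid harm during the rest of PegIFN and all of follow-up. The documents do not support that. Adverse event review and symptom-directed examinations continue on PegIFN and are marked at every off-treatment visit. Section 10.2 allows additional tests at any time, and Section 8.2 lets safety time points be added. Symptomatic thyroid disease has a route to detection and reporting.
- The absence of off-treatment TSH/T4 applies to every participant, so it cannot be counted as a late-starter problem.
- A reader might also infer that the schedule contradicts Section 2.3.1. It does not: the mitigation promises testing according to the schedule, and the schedule includes tests during PegIFN.
- Nor do the documents support a claim of biased thyroid incidence. No thyroid endpoint is defined, thyroid is not among the adverse events of special interest in SAP 4.5.2.1, safety is an exploratory objective, and no comparison of late with on-time starters is planned. Such a comparison would in any case be confounded by exposure (12 to 23 weeks against 24).
- The SAP's summary and listing of out-of-range laboratory values partly answers the reporting point.

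All of this stands and limits the point. It does not supply the closing test, and it does not explain why thyroid function alone, among the main safety assessments, is left out at Off-Treatment Week 1. An out-of-range listing also cannot show a value that was never scheduled.

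**Conclusion.** The point holds as a schedule gap set against a stated mitigation. Every late PegIFN starter misses the Dosing Week 24 TSH/T4, and no later scheduled thyroid test replaces it. The last scheduled test precedes the last planned dose by 2 to 10 weeks if the tests are at Weeks 6, 13 and 24, and by 0 to 11 weeks on a literal column count. The consequence is limited: mainly undetected asymptomatic change, and a Week 24 by-visit summary confined to on-time starters.

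The documents give no late-start share. If 10% to 30% of about 100 participants start late (an assumption), 10 to 30 are affected.

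**What to change.** Reconcile Tables 4, 6 and 7 with the thyroid mitigation in Section 2.3.1, so that the end-of-PegIFN thyroid assessment is tied to the participant's own end of PegIFN and not to column 24. Which visit carries it is for the sponsor to settle. In SAP 4.5.3.1, add a TSH/T4 shift summary from baseline (normal to low or high).

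The cost is one added assay for each participant concerned and one table line.

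Timing matters. The amendment log says that enrolment was complete, and SAP Table 8 projects 47 + 53 = 100 participants at Off-Treatment Week 24 by the January 2023 data cut. For anyone already past the end of PegIFN, a schedule change recovers nothing. The report should then state that late starters have no scheduled end-of-PegIFN thyroid value, and give the number of participants behind each thyroid summary.

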2. INTRODUCTION

2.1. Study Rationale

Chronic hepatitis B (CHB) infection results in progressive liver disease that may lead to complications such as cirrhosis, liver failure, and hepatocellular carcinoma. First-line therapy for CHB is treatment with a nucleoside or nucleotide (nucleos(t)ide) analogue (NA). While these antiviral agents are effective in suppressing hepatitis B virus (HBV) replication in both hepatitis B virus e-antigen (HBeAg)-positive and HBeAg-negative CHB, patients frequently relapse after treatment is discontinued, particularly if hepatitis B virus surface antigen (HBsAg) loss was not achieved. The high rate of relapse in these patients is hypothesised to be due to their inability to raise an effective immune response to the virus in the presence of high circulating levels of HBsAg, which continues to be produced by infected hepatocytes, even in the absence of ongoing viral replication.

Recently, a functional cure of CHB infection has been endorsed as an endpoint for new HBV therapies. Functional cure of CHB infection is defined as sustained loss of HBsAg from serum (with or without anti-HBsAg seroconversion) and undetectable HBV DNA in serum, after completion of a finite course of treatment [Lok, 2017; Cornberg, 2019]. Functional cure occurs in only a very small percentage of patients on NA therapy alone (approx. 3% per annum) [Lok, 2017].

Interferons (IFNs) are a group of immunomodulatory drugs approved as a monotherapy for the treatment of certain patients with CHB. Peginterferons (PegIFN) are indicated for the treatment of adult patients with HBeAg positive and HBeAg negative CHB who have compensated liver disease and evidence of viral replication and liver inflammation. Weekly injections of PegIFN for 48 weeks has been demonstrated to achieve functional cure in a small proportion (up to 9%) of CHB patients as monotherapy, or in combination with nucleosides (off-label) [Marcellin, 2016]. Patients that have lower levels of serum HBsAg before starting treatment with PegIFN have been shown to respond better than those with higher levels in clinical trials [Ren, 2019; Lee, 2018].

GSK3228836 is being developed for the treatment of CHB and is a 2'-O-(2-methoxyethyl)-modified chimeric phosphorothioate antisense oligonucleotide (2'-MOE chimeric ASO) drug targeted to HBV ribonucleic acid (RNA). GSK3228836 is complementary to sequences present in all HBV-derived RNA transcripts and its hybridisation to the cognate RNA results in ribonuclease H-mediated degradation. It is highly specific for HBV RNA transcripts and is not homologous to any regions of the human transcriptome, including either a single nucleotide mismatch or with 17 or more consecutive nucleotide matches. GSK3228836 is an antisense oligonucleotide that is designed to inhibit the synthesis of viral proteins (e.g., HBsAg, HBeAg) by targeting HBV RNA without having a direct effect on HBV covalently closed circular DNA (HBV cccDNA) or integrated HBV DNA. Treatment of patients with CHB with GSK3228836 will permit examination of whether reduction of viral proteins allows resumption of a host immune response against HBV virus and infected cells and if longer treatment with GSK3228836 will result in HBsAg loss leading to sustained suppression of HBV replication after cessation of all treatments for CHB.

Efficacy of 4 weeks treatment with GSK3228836 has been investigated in Phase IIa study, ISIS 505358-CS3, in both treatment naïve participants and participants on stable NA therapy. Both groups of study participants experienced declines in HBsAg, including some achieving HBsAg levels < lower limit of quantification (LLOQ), followed by acute ALT elevations (refer to Investigator's Brochure [GSK Document Number [2019N425040_00](#)]).

The efficacy and safety of GSK3228836 treatment for up to 24 weeks duration is currently being evaluated in a Phase IIb study (Study 209668, NCT04449029). It is hypothesised that additional immunomodulatory therapy (such as PegIFN) may be needed to achieve optimal durable HBsAg loss. Study 209348 is intended to evaluate whether up to 24 weeks of treatment with GSK3228836 followed by 24 weeks of PegIFN can increase the rate of HBsAg loss in participants on stable NA therapy, and whether virologic response can be sustained once PegIFN treatment is discontinued. Efficacy of sequential therapy with GSK3228836 and PegIFN will be compared to the response observed with GSK3228836 in the absence of PegIFN in the Phase IIb study, 209668. Study 209348 will also evaluate the safety and tolerability of the treatment regimen.

